8.1.2. Survival Analyses

Time to event endpoints including all-cause mortality, and cardiovascular-related mortality will be analyzed using SAS Proc Lifetest; p-values will be from the log-rank test. For cardiovascular-related mortality, subjects who died for reasons other than cardiovascular (including “indeterminate”) will be designated as censored at the time of death. Subjects who discontinue for transplantation (ie, heart transplantation and combined heart and liver transplantation) or cardiac mechanical assist device will be handled in the same manner as death (as done in the primary analysis).

Kaplan-Meier survival curves for each treatment group along with median survival times (if applicable) will be presented. Kaplan-Meier product limit estimators will be generated. The number of subjects at risk, number of events and number of censored observations through 6, 12, 18, 24, 30 months will be summarized using the “Method=Life” option in PROC LIFETEST.

Time to event endpoints will also be analyzed using Cox proportional hazards model using Proc PHREG with treatment, TTR genotype (variant and wild-type), and NYHA baseline classification (NYHA Classes I and II combined and NYHA Class III) as factors.

For the analyses by NYHA baseline classification, the Cox proportional hazard model will include treatment and TTR genotype. For the analyses by TTR genotype, the model will include treatment and NYHA baseline classification. The Kaplan-Meier survival curves will also be generated for the analyses by NYHA baseline classification and TTR genotype.

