9.3. Analysis of Secondary Endpoints

As a secondary analysis, the components of the primary endpoint (ie, all-cause mortality and frequency of cardiovascular-related hospitalizations) will be analyzed separately. All-cause mortality will be analyzed using SAS Proc Lifetest; p-values will be from the log-rank test. Kaplan-Meier survival curves for each treatment group along with median survival times (if applicable) will be presented.

All-cause mortality will also be analyzed using Cox proportional hazards model with treatment, TTR genotype (variant and wild-type), and NYHA Baseline classification (NYHA Classes I and II combined and NYHA Class III) as factors. Frequency of cardiovascular-related hospitalizations will be analyzed using a Poisson regression analysis with treatment, TTR genotype (variant and wild-type), NYHA Baseline classification (NYHA Classes I and II combined and NYHA Class III), treatment-by-TTR genotype interaction, and treatment-by- NYHA Baseline classification interaction terms as factors adjusted for treatment duration.

Cardiovascular-related mortality will also be analyzed using the Kaplan-Meier and Cox proportional methods described above.

All the analyses on the secondary endpoints described above will additionally be presented by TTR genotype (variant versus wild-type), NYHA Baseline classification, as well as dose (randomized dose group), and will be considered exploratory.

The proportion of subjects who achieved TTR stabilization in each treatment group at Month 1 will be compared using a Cochran-Mantel-Haenszel (CMH) test for proportions stratified by TTR genotype and Baseline severity (NYHA Classes I and II combined and NYHA Class III). The analysis will be performed separately by TTR genotypes (variant and wild-type) using a CMH test for proportions stratified by Baseline severity (NYHA Classes I and II

combined and NYHA Class III). The analysis will also be performed separately by Baseline severity (NYHA Classes I and II combined and NYHA Class III) using a CMH test for proportions stratified by TTR genotypes (variant and wild-type).

Analyses of TTR stabilization at Month 1 by dose (low vs. placebo and high vs. placebo) will be compared using a Cochran-Mantel-Haenszel (CMH) test for proportions stratified by TTR genotype and Baseline severity (NYHA Classes I and II combined and NYHA Class III).

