8.2.3. Secondary Analyses

The "cardiovascular -related mortality" in all analyses, unless otherwise specified, will combine deaths adjudicated as cardiovascular-related with deaths adjudicated as indeterminate.

The cardiovascular-related mortality and all-cause mortality will be analyzed using survival analysis methods detailed in [Section 8.1.2](#).

Frequency of cardiovascular-related hospitalizations will be analyzed using the Poisson regression analyses detailed in [Section 8.1.5](#).

All the analyses on the secondary endpoints described above will additionally be presented by TTR genotype (variant and wild-type), NYHA baseline classification as well as dose (randomized dose group) and will be considered exploratory.

The proportion of subjects who achieved TTR stabilization in each treatment group at Month 1 will be compared using a Cochran-Mantel-Haenszel test detailed in [Section 8.1.6](#).

A similar test of proportion will be done on TTR stabilization at all other time points and considered exploratory. No subgroup analyses will be done at these other time points.

Except for the analyses by dose group, all analyses of the secondary endpoints, including the proposed exploratory analyses of these endpoints will compare the pooled tafamidis group with the placebo group.

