Appendix 1.3. Sample SAS Code for Analyses Described in Sections 8.1.2 – 8.2.6

Sample SAS code to fit the mixed model repeated measures specified in [Section 8.1.3](#) is given below. The response variable Y is the change from baseline at the study visits.

```
PROC MIXED DATA=xxx METHOD=REML EMPIRICAL;  
CLASS pid center trt visit genotype;  
MODEL y= ybase trt visit genotype trt *visit;  
RANDOM int/SUBJECT=center;  
  
REPEATED visit /SUBJECT= pid (center) r type=UN;  
  
RUN;
```

Sample SAS code for the survival analysis specified in [Section 8.1.2](#) is given below.

```
PROC LIFETEST DATA=xxx PLOTS=(s) graphics;  
TIME dur *status(0);  
STRATA trt;  
RUN;  
  
PROC PHREG DATA=xxx;  
MODEL dur*status(0)=trt genotype NYHAbase/ ties=EXACT;  
RUN
```

Sample SAS code for the ANOVA specified in [Section 8.1.4](#) is given below.

```
PROC GLM DATA=xxx;  
CLASS trt genotype NYHAbase;  
MODEL y= trt genotype NYHAbase trt*genotype trt*NYHAbase;  
RUN;
```

Sample SAS code for the Poisson regression specified in [Section 8.1.5](#) is given below.

```
PROC DATA=xxx;  
ln_styyr=log(styyr);* log transformation to normalize duration of participation ;  
RUN;  
  
PROC GENMOD DATA=xxx;  
CLASS trt genotype NYHAbase;  
MODEL y= trt genotype NYHAbase trt*genotype  
trt*NYHAbase/ type 3 dist=poisson link=log offset=ln_styyr;  
RUN;
```

Sample SAS code for the CMH test specified in [Section 8.1.6](#) is given below. In the code below, the variable NYHA_GENOTYPE is obtained from combining NYHA baseline classification and TTR genotype into one variable (with 4 levels).

```
PROC FREQ DATA=xx;
TABLES NYHA_GENOTYPE*TRT*STABILIZED / CMH
RUN;
```

Sample SAS code for the pattern mixture analysis specified in [Section 8.1.5](#) is given below.

```
PROC MIXED DATA=xxx empirical;
CLASS pid visit center trt pattern genotype;
MODEL y= ybase visit trt genotype pattern visit*trt
trt*pattern / solution;
random int/subject=center;
repeated visit /subject= pid (center) r type=UN;
ESTIMATE 'Tafamidis vs placebo Month 30'
trt 1 -1 visit*trt 0 0 0 0 0 0 0 1 -1
trt*pattern 0.5 0.5 -0.5 -0.5 /cl e; * Placebo adjusted LSMEANS of Tafamidis
averaged over the pattern (equal weight=0.5);
run;
```

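### The planned Kaplan-Meier display of cardiovascular mortality censors non-cardiovascular deaths, so if read as absolute risk it slightly overstates cardiovascular death

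*SAP*

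**What the plan says.** SAP section 8.1.2 covers all-cause and cardiovascular mortality together. For the cardiovascular endpoint, "subjects who died for reasons other than cardiovascular (including “indeterminate”) will be designated as censored at the time of death". The section then plans, for both endpoints:

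- the display, where "Kaplan-Meier survival curves for each treatment group along with median survival times (if applicable) will be presented", together with product-limit estimates;
- numbers at risk, events and censored observations through 6, 12, 18, 24 and 30 months;
- testing, where "p-values will be from the log-rank test", and a Cox model;
- Kaplan-Meier curves again by NYHA class and by genotype.

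Heart transplants and assist devices count as deaths, so they are events here and not competing events.

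Protocol section 9.3 agrees: "Cardiovascular-related mortality will also be analyzed using the Kaplan-Meier and Cox proportional methods described above". The sample code in SAP Appendix 1.3 ("TIME dur *status(0" and so on) has one censoring value and no code for a competing event.

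SAP section 8.2.3 defines the endpoint differently. It says cardiovascular mortality "will combine deaths adjudicated as cardiovascular-related with deaths adjudicated as indeterminate", whereas section 8.1.2 censors the indeterminate deaths.

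**The concern.** Kaplan-Meier treats a censored subject as someone who could still have the event later. A subject who has died of another cause cannot. With such deaths censored, one minus Kaplan-Meier answers a hypothetical question: how many would die of cardiovascular causes if nothing else killed them. It is never below the cumulative incidence, and it exceeds it as soon as a non-cardiovascular death precedes a later cardiovascular one. That is plausible in a trial that admits subjects up to age 90.

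What is at stake is how the display is read. Cardiovascular mortality is the first-listed secondary endpoint, and percentages taken from its curve would be set beside the all-cause curve. They would not fit together: Kaplan-Meier risks for cardiovascular and non-cardiovascular death add up to more than the all-cause risk.

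**Working it through.** The plan gives no cardiovascular-mortality risk, event count or power, so there is no stated figure to reproduce.

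**Inputs**
- All-cause 30-month mortality F: 25% placebo, 12.5% tafamidis (Protocol section 9.1).
- Arm sizes: 160 placebo, 240 pooled tafamidis (80 + 160).
- Non-cardiovascular share of deaths q: not in the documents. Assumed 10–40%, because both documents say that most deaths in cardiac amyloidosis are cardiac.
- Assumed: proportional cause-specific hazards, with the same q in both arms unless stated.

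**Formulas.** The total cumulative hazard is −ln(1−F), and the cardiovascular part is (1−q) times that. Hence:
- one minus Kaplan-Meier = 1 − (1−F)^(1−q);
- cumulative incidence = (1−q) × F.

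Example, placebo, q = 20%: 1 − 0.75^0.8 = 20.56%, against 0.8 × 25% = 20.00%.

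| q | Placebo 1−KM | Cumulative incidence | Excess (points) | Tafamidis 1−KM | Cumulative incidence | Excess (points) |
|---|---|---|---|---|---|---|
| 10% | 22.81% | 22.50% | 0.31 | 11.32% | 11.25% | 0.07 |
| 20% | 20.56% | 20.00% | 0.56 | 10.13% | 10.00% | 0.13 |
| 30% | 18.24% | 17.50% | 0.74 | 8.92% | 8.75% | 0.17 |
| 40% | 15.85% | 15.00% | 0.85 | 7.70% | 7.50% | 0.20 |

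In relative terms the excess is 1.4–5.7% on placebo and 0.7–2.7% on tafamidis.

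**Consistency with the all-cause curve.** Placebo, q = 20%: the non-cardiovascular Kaplan-Meier risk is 1 − 0.75^0.2 = 5.59%. The two add to 20.56 + 5.59 = 26.15%, against an all-cause risk of 25%. The cumulative incidences, 20% and 5%, add up exactly.

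**Finite samples.** In 2,000 simulated arms per setting (q = 10–30%), the gap between the two estimators was never negative. Its mean was 0.3–0.75 points on placebo, where the standard error of the Kaplan-Meier estimate is about 3.2 points. On tafamidis it was 0.1–0.2 points, with a standard error of about 2.0.

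**Higher mortality.** Both documents cite a median survival of 41 months from diagnosis for V122I. Taken as exponential, that gives 1 − 0.5^(30/41) = 39.8% at 30 months. At q = 20% the figures are 33.35% against 31.82% (1.5 points); at q = 40%, 26.24% against 23.87% (2.4 points).

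**Difference between arms.** With q = 20% in both arms, Kaplan-Meier shows 20.56 − 10.13 = 10.4 points and cumulative incidence shows 20.0 − 10.0 = 10.0.

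**Test.** The log-rank test was simulated 5,000 times with equal cardiovascular hazards and the non-cardiovascular hazard halved in one arm. It rejected in 5.2% of trials, against a nominal 5%.

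**The case against.** The case for leaving the plan alone has substance.

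- **Planned outputs.** Section 8.1.2 lists curves, product-limit estimates, medians and counts. It names neither 30-month percentages nor a risk difference for this endpoint; those would have to be read off the estimates. The planned event counts, divided by arm size, come close to the crude risk if follow-up is nearly complete. This stands, but the curves would still be published without a caveat.
- **Correct for its purpose.** A Kaplan-Meier curve with other deaths censored describes the cause-specific hazard and sits naturally beside a cause-specific log-rank test. This stands: the curve misleads only when read as absolute risk.
- **Small size.** Ambiguous cases go to the cardiovascular category at adjudication, which pushes q down. At q = 10% the placebo excess is about 0.3 points. This stands.
- **No decision depends on it.** Cardiovascular mortality is outside the alpha-controlled hierarchy, and all-cause mortality, which does not have this problem, is analysed alongside. This stands too.

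A reader might infer more than the documents support:

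- **That the p-value or hazard ratio is biased.** Censoring competing deaths is legitimate for cause-specific tests.
- **That reported medians will be wrong.** At 25% and 12.5% mortality neither arm is expected to reach a median by 30 months, and the SAP promises one only where applicable.
- **That the treatment difference is always inflated.** That follows when q is equal in both arms, but it is not general. With equal cardiovascular hazards and different non-cardiovascular hazards, Kaplan-Meier shows no difference while cumulative incidence does.

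**Conclusion.** The point holds as a minor matter of reporting. The displayed estimate, read as the risk of cardiovascular death, is biased upward, and nothing elsewhere in the protocol or SAP corrects or qualifies it. At the planned mortality the excess is about 0.3–0.9 points on placebo and 0.1–0.2 on tafamidis, well under one standard error. It would reach about 1.5–2.4 points only if 30-month mortality were near 40% and 20–40% of deaths were non-cardiovascular.

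These sizes rest on an assumed non-cardiovascular share and on proportional cause-specific hazards. They also depend on where indeterminate deaths are placed, which the SAP leaves contradictory. The log-rank and Cox analyses, the primary analysis and the all-cause curves are unaffected.

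**What to change.** 1. Reconcile SAP sections 8.1.2 and 8.2.3 on indeterminate deaths before unblinding. Until then the competing event is not defined and cannot be coded.
2. For cardiovascular mortality, present cumulative incidence curves by arm with non-cardiovascular death as a competing event (the EVENTCODE option in PROC LIFETEST), including the curves by NYHA class and genotype. Take any reported percentages of cardiovascular death from these curves.
3. Keep the log-rank test and Cox model, labelled as cause-specific.
4. Keep Kaplan-Meier for all-cause mortality.

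The cost is one more value in the event-status variable, one option in a procedure already planned, a sentence in section 8.1.2, and the reconciliation in step 1. The data are already adjudicated, and no test or sample size changes. The reported cardiovascular risks will be slightly lower.

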10. Subject must have a Screening visit NT-proBNP concentration > 600 pg/mL (the conversion factor from conventional pg/mL to SI units is to divide by 8.45),
11. Subjects must be able to complete > 100 m on the 6-Minute Walk Test at Screening,

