6.2.1. Baseline (Day 1)

Prior to dosing, the following procedures will be completed at the Baseline visit:

1. Review entrance criteria.
2. Randomization.
3. Medical history (updated for changes since Screening visit).
4. Brief Physical Examination with weight.
5. Single 12-lead ECG - prior to any blood pressure measurement or blood collection.
6. Vital signs (systolic and diastolic blood pressure supine and standing, pulse rate supine and standing, respiration rate, and body temperature).
7. Blood and urine sample collection for the following clinical laboratories:
 - a. Hematology;
 - b. Serum Chemistry;

- c. Coagulation (INR, PT);
 - d. Retinol Binding Protein;
 - e. Urinalysis;
 - f. Urine Pregnancy test – for women of childbearing potential.
8. Collect blood sample for TTR stabilization, TTR oligomer concentration, and TTR concentration assays pre-dose.
 9. Collect blood sample for diflunisal concentration ([Section 7.7.3](#)).
 10. Collect Baseline pre-dose blood sample as control for tafamidis concentration.
 11. Collect pharmacogenomic sample.
 12. Collect blood sample for NT-proBNP and troponin I.
 13. 6-Minute Walk Test ([Appendix 4](#)).
 14. Kansas City Cardiomyopathy Questionnaire ([Appendix 1.1](#)).
 15. EQ-5D-3L ([Appendix 2](#)).
 16. Patient Global Assessment ([Appendix 3](#)).
 17. NYHA classification.
 18. Documentation of concomitant medications.
 19. Adverse event reporting.
 20. Hospitalization determination.
 21. Documentation of vital status and transplant or cardiac mechanical assist device status.
 22. Dispense blinded medication.

Subjects will be instructed to take their first tafamidis daily dose of 4 capsules after the completion of the Baseline procedures and to continue dosing 4 capsules each day in the morning until the next study visit.

At the end of the visit, a time will be scheduled for the Week 2 phone call along with the Month 1 appointment. The subject will be instructed not to take their medication at home on the day of the Month 1 visit, but rather wait and take the medication when instructed by the site staff when they arrive at the clinic. A Subject Daily Dosing Diary stating the date and

time of the Month 1 visit will be issued to the subject. The subject will be reminded to return to the clinic with all dispensed study medication wallets.

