9.1. Sample Size Determination

The primary comparison of interest is the pooled tafamidis 20 mg and 80 mg treatment groups vs. placebo. The target sample size is 400 subjects.

A sample size of 400 subjects is based on findings from study Fx1B-201 (a 12-month, open-label study of tafamidis in TTR-CM subjects), TRACS (an observational study with no treatment intervention other than standard of care in TTR-CM subjects), an understanding of current clinical outcomes in this population, and the uncertainty of the assumptions derived from these limited data.

Given that no closed-form sample size estimation solution is available for the primary analysis method, sample size estimation was performed based on simulations.

Sample size assumptions include:

1. All-cause mortality rate of 12.5% for the tafamidis group and 25.0% for the placebo group (ie, a 50% reduction in mortality with treatment).
2. 1.5 cardiovascular-related hospitalizations for the tafamidis group and 2.5 cardiovascular-related hospitalizations for the placebo group.
3. Treatment duration of 30 months.
4. Significance level (alpha) of 0.05 (two-sided test).

With these assumptions, 300 subjects (n=120 for placebo, n=60 for 20 mg, n=120 for 80 mg) yields a power of over 90% for the primary comparison. A more conservative assumption of 30% reduction in mortality (17.5 % for tafamidis and 25% for placebo) yields a power of approximately 80%. With an assumption of 30% reduction in mortality and increasing the number of subjects to 400 subjects (n=160 for placebo, n=80 for 20 mg, and n=160 for 80 mg) yields a power of approximately 90%.

Summary of operating characteristics:

| Assumptions | Sample Size | Power |
|--|--------------------|--------------|
| 50% mortality reduction, hosp frequency 2.5 (pbo), 1.5 (taf) | N=300 | 96% |
| 30% mortality reduction, hosp frequency 2.5 (pbo), 1.5 (taf) | N=300 | 80% |
| 30% mortality reduction, hosp frequency 2.5 (pbo), 1.5 (taf) | N=400 | 90% |

pbo=placebo, taf=tafamidis

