8.1.5. Poisson Regression for Frequencies

Frequency of cardiovascular-related hospitalization and frequency of all-cause hospitalization will be analyzed using Poisson regression analysis with *treatment, TTR genotype (variant and wild-type), NYHA Baseline classification (NYHA Classes I and II combined and NYHA Class III), treatment-by-TTR genotype interaction, and treatment-by-NYHA Baseline classification interaction terms as factors adjusted for treatment duration.*

For the subgroup analyses by NYHA classification (NYHA Classes I and II combined and NYHA Class III), the Poisson regression analysis will have treatment, TTR genotype (variant and wild-type), and treatment-by-TTR genotype interaction terms as factors adjusted for treatment duration.

For the subgroup analyses by TTR genotype, the Poisson regression analysis will have treatment, NYHA baseline classification, and treatment-by- NYHA baseline classification (NYHA Classes I and II combined and NYHA Class III) as factors adjusted for treatment duration.

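### The Cox mortality models and Poisson hospitalisation models leave out baseline NT-proBNP and 6-minute walk distance, giving up a small and nearly free gain in efficiency

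*SAP*

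**What the plan says.** **Mortality.** SAP 8.1.2 and Protocol 9.3 take the p-value from the log-rank test. The sample code in SAP Appendix 1.3 lists treatment alone in the STRATA statement, so that test is unadjusted. The Cox model is additional: "Time to event endpoints will also be analyzed using Cox proportional hazards model using Proc PHREG with treatment, TTR genotype (variant and wild-type"), plus NYHA class grouped as I/II v III. Protocol 9.3 agrees: "All-cause mortality will also be analyzed using Cox proportional hazards model with treatment, TTR genotype (variant and wild-type"), with the same NYHA grouping.

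**Hospitalisation.** SAP 8.1.5: "Frequency of cardiovascular-related hospitalization and frequency of all-cause hospitalization will be analyzed using Poisson regression analysis with" treatment, genotype, two-level NYHA class, the two treatment interactions and an adjustment for duration. The code is a log-link Poisson model with an exposure offset and no dispersion term.

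**Reason given.** SAP 6.4 lets NYHA class stand for severity where an endpoint has no baseline score of its own. SAP 8.1.3 uses the endpoint's own baseline score where there is one.

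**What is measured.** Protocol 4.1: "Subject must have a Screening visit NT-proBNP concentration > 600 pg/mL", with no upper limit, and a Screening 6MWT above 100 m. Protocol 6.2.1 repeats both before dosing ("Collect blood sample for NT-proBNP and troponin I", and the walk test as the next item).

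**The concern.** Severity enters these models as one two-level clinician grade, with Class IV excluded at entry. Two quantitative severity measures exist for every eligible subject and are not used. That an endpoint lacks a baseline value of its own is no reason to set aside severity that was measured.

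Randomisation does little to compensate. It is stratified by NYHA I v II/III, and the SAP's Amendment 3 entry reports very few Class I subjects, so chance imbalance in severity is left to the analysis models.

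These models supply effect estimates for the two components of the primary endpoint. At stake are the efficiency of the Cox estimate and its own test, and the unexplained between-subject variation left in the hospitalisation model.

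**Working it through.** **1. The plan's own power figures.** Protocol 9.1 gives "Significance level (alpha) of 0.05 (two-sided test") and power of 96% (N=300, 50% mortality reduction), 80% (N=300, 30%) and 90% (N=400, 30%). These belong to the Finkelstein-Schoenfeld test. Simulating T/√V as in SAP 8.1.1 (four strata, exponential deaths, no dropout, 6,000 trials each) gives 96.0%, 80.1% and 90.0%. This assumes stratum shares of 37.5/37.5/12.5/12.5% and gamma-Poisson counts with dispersion 1, neither of which is in the documents. With pure Poisson counts all three exceed 99%. Neither the Cox nor the Poisson model enters this calculation.

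**2. Mortality alone, N=400 (160 placebo, 240 pooled tafamidis).** Inputs: "All-cause mortality rate of 12.5% for the tafamidis group and 25.0% for the placebo group", and "A more conservative assumption of 30% reduction in mortality (17.5 % for tafamidis and 25% for placebo) yields a power of approximately 80"%. Assuming exponential hazards, HR = ln(1−p₁)/ln(1−p₀), and Schoenfeld power = Φ(√(d × 0.6 × 0.4) × |ln HR| − 1.96).
- 17.5% v 25%: d = 160×0.25 + 240×0.175 = 82; HR = ln 0.825/ln 0.75 = 0.669; power = Φ(4.436×0.402 − 1.96) = 43%.
- 12.5% v 25%: d = 40 + 30 = 70; HR = 0.464; power = Φ(4.099×0.768 − 1.96) = 88%.

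**3. Cox model with and without a severity score.** Let x be a standard normal score holding what NT-proBNP and 6MWT together add beyond genotype and NYHA, with log-hazard s·x. The documents give no value for s, so it is varied. For each s the arm hazards are solved so that 30-month mortality stays at the protocol's figures. There are 2,000 trials per setting, and both models are fitted to the same data. Genotype and NYHA are in both models but carry no effect in the simulation. The Monte Carlo SE of each power is about 1.1 points.

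Results at 17.5% v 25% (median HR):

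| s | HR per SD (eˢ) | HR planned | HR adjusted | Power planned | Power adjusted | Gain (points) |
|---|---|---|---|---|---|---|
| 0.3 | 1.35 | 0.666 | 0.661 | 44.7% | 46.3% | 1.6 |
| 0.5 | 1.65 | 0.667 | 0.659 | 44.2% | 46.5% | 2.3 |
| 0.7 | 2.01 | 0.666 | 0.646 | 45.0% | 49.4% | 4.4 |
| 1.0 | 2.72 | 0.669 | 0.627 | 43.7% | 55.5% | 11.8 |

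At 12.5% v 25%, power moves from 88.7% to 90.4% (s=0.5), 89.5% to 92.4% (0.7) and 89.3% to 94.7% (1.0).

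The planned HR stays at the value implied by the protocol's mortality rates at every s; it is the adjusted HR that moves away from 1. The mean SE of the log HR hardly changes (0.223 v 0.225 at s=1.0), so the power gain comes from the more conditional effect.

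**4. Poisson model.** Counts have mean 2.5 on placebo and rate ratio 1.5/2.5 = 0.60, with the same design, main effects only and full exposure. The median rate ratio is 0.60 with or without the score at every s from 0 to 1.0. What changes is the variance. At a true ratio of 1 and s=0.7, the planned model reports an SE of 0.065 against an empirical 0.105, and type I error is 23%; at s=1.0 it is 37%. With the score included it is about 5%, but only because the score is the sole heterogeneity in this simulation. At ratio 0.60 with a correct SE, power without the score is Φ(0.511/0.109 − 1.96) = 99.7% at s=0.7 and Φ(0.511/0.151 − 1.96) = 92% at s=1.0.

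**The case against.** The best case for leaving the plan alone has four parts.

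- **The choice is deliberate and consistent.** SAP 6.4 states a rule, Amendment 3 revisited the NYHA grouping, and genotype and NYHA are also the strata of the primary test. This stands as an explanation. It gives no reason against using measured severity as well.
- **The gain is small and rests on an assumption.** This stands. Up to s=0.7 it is about 2 to 4 points on a test with roughly 45% power. A double-digit gain needs an HR near 2.7 per SD beyond genotype and NYHA, and nothing in the documents supports that.
- **No controlled inference is touched.** This stands. Mortality and hospitalisation as separate endpoints are secondary, without alpha control (Protocol Summary), and the mortality p-value is from the log-rank test.
- **The change costs more than one line.** This stands in part. The functional form of 6MWT must be fixed, and the subgroup models have fewer events. Limiting the change to the overall models answers the second point. With 70 to 82 expected deaths, five Cox parameters leave 14 to 16 deaths per parameter. Cardiovascular deaths will be no more numerous, and the documents do not give their share.

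**Conclusion.** The point holds as an avoidable loss of efficiency in secondary models. It is not an error or a contradiction in the plan. The Cox loss is about 2 to 4 power points at s of 0.3 to 0.7 in the 30% reduction scenario and about 12 at s=1.0. It depends on a prognostic strength that the documents do not supply, and on exponential hazards without dropout.

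Four stronger readings are tempting and are not supported:
- **That the planned hazard ratio is biased.** The difference is non-collapsibility: the planned HR validly estimates a less conditional effect.
- **That the hospitalisation rate ratio is pulled towards 1.** A log-link rate ratio is collapsible, and the simulation returns 0.60 either way.
- **That the mortality p-value would improve.** It comes from the log-rank test, which extra Cox terms do not alter.
- **That the trial's stated power is affected.** The 96/80/90% figures concern the Finkelstein-Schoenfeld test alone.

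For hospitalisation, the covariates would remove only part of the unexplained variation. The missing dispersion term is the larger weakness, and adding covariates does not replace it.

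**What to change.** Before unblinding, amend SAP 8.1.2 and 8.1.5 so that the overall Cox models (all-cause and cardiovascular mortality) and the overall hospitalisation models add log(baseline NT-proBNP) and baseline 6MWT distance to genotype and NYHA class. Use the Screening value where the Baseline value is missing, and state the functional form of 6MWT. Report the currently planned models alongside as a sensitivity analysis. Leave the subgroup models as they are. Give the hospitalisation model a robust or dispersion-adjusted variance, or use a negative binomial model. State explicitly whether the log-rank test is stratified.

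**Cost.** Two terms per model and no new data. Protocol 9 allows the SAP to make this change without a protocol amendment, since the primary endpoint and its analysis are untouched, and SAP section 1 records the study as still blinded. The downside is small: the reported HR becomes conditional on two more covariates and must be labelled so, and it will sit beside a log-rank p-value that does not change.
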